# **OXYGENATE**

## **(nO aXillarY surGEry iN early breAsT cancEr international prospective registry study)**

Prospective multicenter registry specifically for patients who have undergone surgery for primary breast cancer without undergoing sentinel lymph node biopsy. The main objective of this registry is to collect detailed, real-world data on the outcomes of this therapeutic approach, providing information on its clinical effectiveness when sentinel lymph node biopsy is omitted.

## 1. Background

For many decades, sentinel lymph node biopsy (SLN) has been the standard of care in early breast cancer. In recent years the publication of the ACOSOG Z0011, (1, 2) showed that there was no advantage in performing axillary lymph node dissection (ALND) compared with not performing ALND, even when up to 2 sentinel nodes are positive, for patients receiving breast-conserving surgery, adjuvant radiotherapy, and medical treatment. In the study, 23.7% of the control group (ALND) patients had additional metastatic lymph nodes other than sentinel nodes. However, the axillary recurrence rate or DFS did not differ in the SLN only and control groups. (1) These findings raise questions about the need to remove sentinel lymph nodes, especially in patients who undergo breast-conserving surgery and whole-breast radiation.

The Sentinel Node versus Observation after Axillary Ultrasound (SOUND) trial was a prospective, multi-national noninferiority phase 3 study, which randomized patients with a negative preoperative axillary ultrasound (US) to SLN or no axillary surgery, prior to breast conserving surgery (BCS). (3) The primary focus of the study was to determine the oncological outcomes in patients with negative ultrasound results who avoided SLN. The results showed that there were no significant differences in survival or axillary recurrences. The cumulative incidence of isolated axillary recurrences at 5 years was 0.4% in the no-axillary surgery arm. In the whole cohort, only 2% of patients developed a distant relapse, 1% developed a local breast relapse, and 1% developed contralateral breast cancer. Interestingly, the diagnosis of other malignancies unrelated to breast cancer (approximately 3%) was the most frequent oncological outcome. (3)

Furthermore, only 13.7% of the patients treated with SLN had positive lymph nodes, with 11.7% having just one. Patients have only a likelihood of 0.6% of having four or more positive nodes, and therefore should not be treated with ALND in case a positive SLN is found.

Other international trials have backed up these findings. Both the NAUTILUS (4) trial and the INSEMA (5) trial confirmed that management of patients with N0 on ultrasound can be carried out without axillary surgery, leading to improved survival outcomes and fewer complications. Likewise, omission of axillary surgery was reported to be both safe and improve health-related quality of life in the IIT 2015-06 Chung-SNBO trial(6) in South Korea and the BOOG 2013-08 study (7) in the Netherlands. The totality of the evidence from these studies suggests that in early-stage breast cancer, the minimally invasive approach with omission of sentinel lymph node biopsy can be a suitable solution that improves postoperative outcomes for patients.

Axillary ultrasound (AUS) is the method of choice worldwide to assess lymph node involvement in patients with known or suspected breast cancer.(8) With advances in imaging techniques, the accuracy of AUS to predict axillary status with or without node biopsy has increased significantly. According to the literature, US can be highly specific if morphologic characteristics are used, with a sensitivity ranging from 26% to 76% and a specificity of 88%–98% for nonpalpable metastatic lymph nodes. (9) The accuracy of AUS can be improved with image guided biopsy.

With the publication of the SOUND and the INSEMA trial, several questions have been raised related to the selection of adjuvant treatment in those patients with omitted SLN.

The changing in clinical practice after the publication of these trials are being implemented and, in some Institutions, patients with a negative clinical exam and negative axillary ultrasound, postmenopausal, age  $\geq 50$  years, with grade 1–2, ER positive  $> 10\%$ , T1, non-lobular invasive breast cancers and a Ki-67  $< 20\%$  , no longer require SLNB. (10)

This group of patients are the ones who most benefit from PBI, so the dilemma is whether patients who comply with the selection criteria for these trials can be treated with PBI considering that the SOUND trial included only 10% of patients treated with PBI.

Looking at the data in the SOUND trial, adjuvant radiotherapy and hormonal treatment are administered for most of the patients. Precisely, about 98% took hormone therapy, and 98% of patients underwent postoperative radiotherapy. Among these, 10% underwent partial breast irradiation (PBI), while the remaining portion got whole breast irradiation (WBI). (3)

For early-stage breast cancer, it has been repeatedly observed that most ipsilateral breast tumor recurrence occur in the original tumor bed.(11) The highest benefits of whole breast irradiation (WBI) seems to result from the dose delivered in the tissue surrounding the tumor bed. Nonetheless, the challenge is to reduce treatment morbidity while maintaining the ability to decrease local recurrences. As a result, techniques such as breathing-adapted image-guided RT and partial-breast irradiation (PBI) have been developed to reduce toxicity without compromising the oncologic outcomes. (12)

PBI can be delivered through different techniques that include both external beam RT (EBRT), intraoperative RDT and brachytherapy. PBI has become widely used in the treatment of early-stage, low-risk breast cancer, as it has shown equivalencies in terms of local control and overall good cosmetic outcomes. (13)

With the publication of the SOUND and the INSEMA trial, several questions have been raised related to the selection of adjuvant treatment in those patients with omitted SLN.

The changing in clinical practice after the publication of these trials are being implemented and, in some Institutions, patients with a negative clinical exam and negative axillary ultrasound, postmenopausal, age  $\geq 50$  years, with grade 1–2, ER positive  $> 10\%$ , T1, non-lobular invasive breast cancers and a Ki-67  $< 20\%$ , no longer require SLNB. (10)

This group of patients are the ones who most benefit from PBI, so the dilemma is whether patients who comply with the selection criteria for these trials can be treated with PBI considering that only the SOUND trial has 10% of patients treated with PBI.

These findings are particularly timely in the context of results from the IMPORT LOW study that have been reported, showing the non-inferiority of PBI compared to WBI after breast-conserving surgery in cohorts similar to those enrolled in the SOUND study. (14) Data from the PBI group in the IMPORT LOW study show that at 5 and 10 years, the cumulative incidences of local recurrence were 0.5% and 2.8%, respectively, indicating long-term effectiveness of PBI in preventing local recurrences, as also confirmed by the ASTRO guidelines. (14, 15)

In oncology, real-world data (RWD) and real-world evidence (RWE) are rapidly emerging as common sources of information for patients, clinicians, and regulators. Randomized controlled trials (RCTs) reduce bias and confounding through the randomization process and provide the highest quality of evidence regarding efficacy. But given the inherent differences between observational data and clinical trial results, RWD may still have independent value as complementary tools to trial results. (16) Once that there is robust evidence that the omission of SLN in early stage breast in selected patients works, the question is whether it does work in real world practice within the different practices and policies.

Our study will establish a prospective cohort study as an international registry of all those patients who undergo BCS for primary breast cancer without SLN to assess outcomes in real world. The next challenge is to better understand which patients with no axillary surgery and early-stage breast cancer have similar outcomes focusing on the radiation therapy and the systemic treatment option for each patient.

This will be a very large dataset of value to clinicians and researchers worldwide. From this information, we hope to be able to refine breast cancer management practices, improve the care of

patients, and assess whether the less-invasive approach can be recommended for more patients without compromising oncologic outcomes. This registry will serve to help further the precision in the management of breast cancer patients, affording them ideal care and minimizing the encumbrance of undue invasive procedures.

## **2. Purpose and Outcomes**

Our prospective study will establish a comprehensive international registry specifically for patients who have undergone surgery for primary breast cancer without SLNB. The main objective of this registry is to gather detailed, real-world data on the outcomes of this particular treatment approach, providing insights into the clinical efficacy and quality of life of patients when SLNB is omitted.

## **3. Study aims**

### Primary endpoint

Evaluation of the 3-year axillary recurrence rate

Evaluation of the 5-year invasive disease-free survival (iDFS)

### Secondary endpoints

Evaluation of different type of radiation therapy

Evaluation of different type of systemic treatment

Evaluation of outcomes based on histologic stage and subtype

## **4. Inclusion and Exclusion Criteria**

### 4.1 Inclusion criteria

- Any age
- cT1-2
- cN0 Negative preoperative assessment of the axilla (ultrasound with or without FNAC /Core biopsy in case one doubtful node is found)
- Breast surgery as first treatment
- **No axillary surgery**
- Multifocal/ multicentric breast cancer
- Candidates to receive breast conserving surgery
- Written informed consent must be signed and dated by the patient and the investigator prior to inclusion.
- Patients must be accessible for follow-up.

#### ***4.2 Exclusion Criteria***

- Synchronous distant metastases
- **Any axillary surgery**
- Neoadjuvant treatment
- Previous malignancy
- Bilateral breast cancer
- Previous primary systemic therapy
- Pregnancy or breastfeeding
- Pre-operative diagnosis (cytology or histology) of axillary lymph node metastases
- Pre-operative radiological evidence of multiple involved or suspicious nodes
- Patients with psychiatric, addictive, or any disorder, which compromises their ability to give informed consent for participation in this study.

#### **Statistical analysis**

A sample size calculation was performed to determine the number of participants required for a non-inferiority study comparing the experimental group to the general population. The reference axillary recurrence rate was set at 0.3% based on population data, while the expected recurrence rate in the experimental group was 1.0%, as reported in published studies. A significance level of 5% and a statistical power of 80% were used. The analysis determined that 744 participants were required. To account for potential dropouts and exclusions, the sample size was increased by 10%, resulting in a final adjusted sample size of 827 participants.

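### The 744 patients size a test for a difference from 0.3%, not a non-inferiority comparison: no margin is stated, and the 80% is power to show a higher recurrence rate

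*Protocol*

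**What the plan says.** The unnumbered Statistical analysis section, between sections 4.2 and 5 of the protocol, describes the calculation as giving the number "required for a non-inferiority study comparing the experimental group to the general population". Its inputs are:

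- Reference: "The reference axillary recurrence rate was set at 0.3% based on population data".
- Expected: "the expected recurrence rate in the experimental group was 1.0%, as reported in published studies".
- Error rates: "A significance level of 5% and a statistical power of 80% were used".

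The result is "The analysis determined that 744 participants were required", raised to 827 for dropouts and exclusions.

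The protocol gives no margin, upper limit, null or alternative hypothesis, or sidedness, in this section or elsewhere. Neither rate has a time horizon, although section 3 makes the 3-year axillary recurrence rate a primary endpoint. Section 5 describes one prospective cohort of consecutive patients with no concurrent control.

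**The concern.** A non-inferiority sample size depends on how far the acceptable limit lies from the rate expected in the cohort. Here there is no limit, and the expected rate is more than three times the reference (1.0/0.3 = 3.3). With only these two rates, the obvious calculation is a test of whether the cohort differs from 0.3%, which reverses the stated aim.

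This matters because axillary recurrence is the only primary endpoint that is sized. A significant result against 0.3% would show a higher recurrence rate. A non-significant one could be taken as support for non-inferiority when it is only absence of evidence. For a registry meant to inform whether omitting axillary surgery can be extended to more patients, that risks false reassurance.

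**Working it through.** **Inputs** (all from Statistical analysis): p0 = 0.003, p1 = 0.010, significance 5%, power 80%. Sidedness is not stated, so both forms were tried.

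**1. Reproducing the protocol's figure.** One-sample test of a proportion against a fixed value, normal approximation:

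n = [z(1−α/2)·√(p0(1−p0)) + z(0.80)·√(p1(1−p1))]² / (p1−p0)²

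= [1.960 × 0.05469 + 0.8416 × 0.09950]² / 0.007²

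= [0.10719 + 0.08374]² / 0.000049 = 743.97, so **744**.

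Then 744/0.9 = 826.7, so **827**. Both published figures match to the patient. The one-sided 5% version gives 616.

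The null here is a rate of 0.3% and the alternative is 1.0%, so power is the probability of concluding that the rate differs from 0.3% when it is 1.0%, that is, that it is higher.

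**2. The same formula with non-inferiority hypotheses.** Suppose 1.0% is the limit (null) and 0.3% the truth:

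- One-sided 5%: [1.645 × 0.09950 + 0.8416 × 0.05469]² / 0.007² = 897.3, so **898**.
- One-sided 2.5%: [1.960 × 0.09950 + 0.8416 × 0.05469]² / 0.007² = 1,185.7, so **1,186**.

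Neither is 744. A two-arm non-inferiority calculation with 0.3% in both arms and a 0.7-point margin gives 755 per arm at one-sided 5%. It needs a concurrent control and a true rate that the protocol does not assume.

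**3. Power for the test actually sized (exact binomial, n = 744).** Expected events are 2.2 at 0.3% and 7.4 at 1.0%, so the normal approximation is rough.

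| Reject 0.3% if | Upper-tail α | Power at 1.0% |
|---|---|---|
| 6 or more events | 0.026 | 75% |
| 7 or more events | 0.008 | 61% |

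Conversely, at a true 1.0% the test is non-significant with probability 25% (5 or fewer events) or 39% (6 or fewer).

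**4. The limit at which 744 has at least 80% non-inferiority power, if the truth is 1.0%.** By exact binomial, success must allow 10 events: P(X ≤ 10) = 87% at 1.0%, while P(X ≤ 9) = 78%. The exact upper limit for 10/744 is 2.27% (one-sided 5%) or 2.46% (one-sided 2.5%). Against the reference, 2.27/0.3 = 7.6 and 2.46/0.3 = 8.2. The normal approximation gives 2.2% and 2.4%.

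**5. Reading the 0.7-point gap as the margin (limit 1.0%).** This is an assumption, as the protocol does not say it. With 744 patients, 2 events give an exact one-sided 97.5% upper limit of 0.97%. Three events exceed 1.0% at either level (1.04% at one-sided 5%, 1.17% at 2.5%). So at most 2 events are allowed:

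| True rate | P(X ≤ 2) |
|---|---|
| 0.3% | 61% |
| 0.4% | 43% |
| 1.0% | 2% |

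The 2% follows from the truth lying on the limit, where success cannot exceed α. It shows that this reading is incompatible with the expected rate. The 0.4% row uses the Background figure ("The cumulative incidence of isolated axillary recurrences at 5 years was 0.4% in the no-axillary surgery arm"), which has a different horizon and definition from the 3-year endpoint and is only illustrative.

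**The case against.** **The two-sided difference test is inferred.** The protocol states neither hypotheses nor sidedness. That is so, but the formula matches 744 and 827 to the patient. Two other variants come close without matching: the one-sided test with continuity correction (752) and the one-sided arcsine test (751). Both are also tests for a difference.

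**No decision rule is stated, and the statistical analysis plan is not at hand.** The section sizes the study but does not say how the endpoint will be tested, and section 3 speaks only of evaluating the rate. The risk that a non-significant result is read as non-inferiority is therefore a possibility, and the 25% to 39% depends on it. This limits the consequence but does not remove the error. The calculation is complete in the protocol, and a margin set later cannot turn 744 into the result of a different calculation.

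**Some figures rest on an unstated margin.** This stands for the 1.0%-limit figures, which are conditional. The limit of about 2.3% to 2.5% needs only the protocol's expected rate, its sample size and a choice of one-sided level.

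**This is a non-interventional registry.** No treatment is allocated on the strength of this calculation, and 744 patients still give useful precision. The harm is to interpretation, not to conduct. That makes the repair cheap, but a non-inferiority claim without a margin remains a substantive defect.

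**Conclusion.** The concern holds. The stated inputs give 744 as the size of a test for a difference between 0.3% and 1.0%. The 80% is power to show a higher rate, and only by normal approximation (61% to 75% exact). The protocol has no non-inferiority margin, and its claimed power for non-inferiority has no basis.

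If the truth is 1.0%, as the protocol expects, 744 supports a non-inferiority conclusion with at least 80% power only for a limit near 2.3% (one-sided 5%) or 2.5% (one-sided 2.5%), which the protocol neither states nor justifies. If 1.0% was meant as the limit with a true 0.3%, the same formula needs 898 or 1,186. These figures assume 744 evaluable patients, a binomial endpoint and a fixed reference; the two-sided form of the original test is inferred from the exact match.

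**What to change.** Rewrite the sample size paragraph by amendment, in one of two ways.

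- **Estimation.** Drop the non-inferiority label, call the study single-arm estimation, and state the precision 744 gives by exact 95% CI: 3 events = 0.40% (0.08% to 1.17%); 7 events = 0.94% (0.38% to 1.93%).
- **Non-inferiority.** State and justify an absolute upper limit for the 3-year rate. Declare non-inferiority only if the exact one-sided upper confidence limit lies below it. Give the one-sided level, the assumed true rate and the power that 744 provides. The sponsor must choose the limit.

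In either case, state that a non-significant test against 0.3% is not evidence of non-inferiority. Give both rates a time horizon matching the 3-year endpoint. Replace the general population with a defined reference and its source; patients treated with sentinel node biopsy and otherwise comparable would be a natural candidate.

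The cost is one reworded paragraph and no extra patients. The stated power becomes less favourable or gives way to a precision statement.

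### The stated 80% power at 744 participants rests on a normal approximation with 2 to 7 expected events; exact power is 61% to 75%, depending on a hypothesis and sidedness that are not stated

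*Protocol*

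**What the plan says.** The sample size paragraph (Protocol, unnumbered Statistical analysis section after 4.2) describes a "non-inferiority study comparing the experimental group to the general population". Its inputs are:

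- Reference: "The reference axillary recurrence rate was set at 0.3% based on population data".
- Expected: "the expected recurrence rate in the experimental group was 1.0%, as reported in published studies".
- Error rates: "A significance level of 5% and a statistical power of 80% were used".
- Result: "The analysis determined that 744 participants were required".
- Dropout: "the sample size was increased by 10%, resulting in a final adjusted sample size of 827 participants".

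The endpoint concerned is the first of the two primary endpoints in section 3: "Evaluation of the 3-year axillary recurrence rate". The paragraph does not give the null hypothesis, a non-inferiority margin or limit, the sidedness of the 5%, the test, or whether the calculation was exact or approximate.

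**The concern.** Rates of 0.3% and 1.0% in some 740 patients mean single-figure event counts. At such counts the binomial distribution is skewed and moves in coarse steps, so a normal approximation can misstate both size and power. If 744 came from such a formula, the 80% is a property that the design does not have.

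This matters because axillary recurrence is a primary endpoint and the only one behind the sample size. A reader who trusts 80% would misjudge how often the registry could end without a conclusive result by chance alone. A later analysis plan can choose the test, but it cannot make 744 patients deliver a power that they do not have.

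**Working it through.** **Inputs (Protocol, Statistical analysis).** Reference 0.3%, expected 1.0%, significance 5%, power 80%, n = 744, dropout 10%.

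**1. Reproducing 744.** One-sample normal approximation with p0 = 0.003, p1 = 0.010, two-sided 5% (z = 1.96) and 80% power (z = 0.8416):

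n = [1.96·√(0.003·0.997) + 0.8416·√(0.010·0.990)]² / 0.007² = 743.97, so 744.

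Then 744 / 0.9 = 826.7, so 827. Both stated figures are recovered. One-sided 5% in the same formula gives 616. One-sided 5% with a continuity correction gives 752, and with the arcsine transformation 751. Taking 1.0% as the null and 0.3% as the truth gives 1,186 (two-sided 5%) or 898 (one-sided 5%). The exact match identifies the method by inference: a test for a difference from 0.3% when the truth is 1.0%.

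**2. Expected events at 744.** 744 × 0.003 = 2.2; 744 × 0.010 = 7.4.

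**3. Cut-off of the z-test behind the formula.** Upper critical value: 744·0.003 + 1.96·√(744·0.003·0.997) = 5.16, so it rejects at 6 or more events. The lower critical value is −0.69, so it cannot reject on the low side.

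**4. Exact binomial size and power at 744.**

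| Framing | Rule | Size | Power |
|---|---|---|---|
| z-test behind 744, or one-sided 5% exact test, null 0.3%, truth 1.0% | 6 or more events | 2.6% | 75.3% |
| Equal-tailed two-sided 5% exact test, null 0.3%, truth 1.0% | 7 or more events | 0.8% | 61.5% |
| Non-inferiority, limit 1.0%, truth 0.3%, one-sided 2.5% or 5% | at most 2 events | 2.1% | 61.4% |

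A two-sided exact test that orders outcomes by their probability also rejects at 6 events (p = 0.026; at 5 events p = 0.076) and so has the same 75.3%. In the non-inferiority row, moving to one-sided 5% changes nothing, because allowing 3 events has size 6.1%.

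**5. If all 827 were evaluable.**

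| Framing | Rule | Size | Power |
|---|---|---|---|
| One-sided 5% exact, null 0.3%, truth 1.0% | 6 or more | 4.1% | 83.4% |
| Equal-tailed two-sided 5% exact, null 0.3%, truth 1.0% | 7 or more | 1.4% | 72.0% |
| Non-inferiority, limit 1.0%, truth 0.3%, one-sided 2.5% | at most 2 | 1.1% | 54.9% |
| Non-inferiority, limit 1.0%, truth 0.3%, one-sided 5% | at most 3 | 3.5% | 76.2% |

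At 827 the z-test's critical value is 5.56, so it too rejects at 6 or more and shares the 83.4%.

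**6. A reading left out.** If 1.0% were both the true rate and the limit, power would equal the size, about 2%. That is not a workable design and is not counted among the framings above.

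**The case against.** The strongest objection is that no single exact power can be set against the 80%, because the paragraph leaves sidedness and direction open. A reader might infer that power is 61% however the hypothesis is framed. The documents do not support that. A 2.5% limit per tail is not written anywhere in the paragraph. At 744 no low-side rejection against 0.3% is possible, since zero events has probability 10.7%. The rule of 6 or more events therefore has total size 2.6%, inside the stated 5%, and power 75.3%. Measured on the test that yields 744, the loss due to the approximation is about 5 points. The two 61% figures agree only because of where the discrete cut-offs fall.

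A reader might also infer that the registry has a success criterion turning on 2 versus 3 events, which it would miss about 4 times in 10 at a true rate of 0.3%. That describes a non-inferiority test against 1.0%, which the paragraph does not write down. In that direction the shortfall is not mainly an approximation error either: the normal formula itself asks for 898 to 1,186 patients.

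Nor can the Background figure ("The cumulative incidence of isolated axillary recurrences at 5 years was 0.4% in the no-axillary surgery arm") serve as a planning value. It is a 5-year rate of isolated recurrence, whereas the endpoint is at 3 years and not restricted to isolated events.

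Finally, this is a non-interventional registry, and the choice of an exact test can be left to an analysis plan. That is fair as to the test. But rates, significance level, power and sample size are all stated in the protocol, and they do not fit together under any of the framings in step 4. That part stands.

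**Conclusion.** The concern holds in bounded form. At 744 evaluable patients the stated 80% is not met: exact power is about 75% for the test that the formula implies (or a one-sided 5% exact test against 0.3%), and about 61% for an equal-tailed two-sided 5% exact test or for non-inferiority against 1.0% with a true rate of 0.3%. It would be too strong to say that no framing reaches 80% at 827: a test for a rate above 0.3% that rejects at 6 events gives 83%. But that requires none of the dropout for which the number was inflated, and a positive result there would show recurrence above the reference, which is not a non-inferiority conclusion.

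The conclusion assumes a simple binomial count among evaluable patients at 3 years and takes the protocol's two rates as given. That the number came from a normal approximation is inferred from the exact match. The exact power at 744 does not depend on that inference.

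**What to change.** In the Protocol's Statistical analysis paragraph:

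- State the null hypothesis, the limit or margin, the assumed true rate and the sidedness.
- Replace the 80% with the exact binomial power at 744 for that choice: about 61% for non-inferiority against 1.0% with truth 0.3%, or about 75% if the test against 0.3% is kept at one-sided 5%.
- Give the decision rule as a number of events. For example, under the non-inferiority framing, at most 2 axillary recurrences among 744 evaluable patients would rule out 1.0%, with size 2.1%.
- Name an exact test and interval for the analysis.

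The cost is one reworded paragraph and a less favourable stated power. Correcting the statement needs no extra patients. If the sponsor prefers to keep 80%, the evaluable numbers from which exact power stays at or above 80% are 906 (one-sided 5% against 0.3%), 1,022 (equal-tailed two-sided 5%), 1,049 (non-inferiority, one-sided 5%) and 1,303 (non-inferiority, one-sided 2.5%), each before the 10% dropout allowance.
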